### **2.2 Secondary Objectives**

- To evaluate the tolerability of deferiprone DR tablets in two different dosage groups in patients with systemic iron overload
- To evaluate the acceptability to patients of deferiprone DR

The endpoints for the secondary objectives provided in [Section 9.1.2](#).

## **3 STUDY DESIGN**

### **3.1 Description of Study Design**

This is a multi-center open-label study in patients with transfusion-dependent blood disorders who are currently taking deferiprone immediate release tablets (Ferriprox) for the treatment of systemic iron overload. There will be two treatment groups, defined as “low dosage” (Group A) and “high dosage” (Group B). With Ferriprox, the recommended starting dosage is 75 milligrams per kilogram of body weight (mg/kg) per day and the recommended maximum is 100 mg/kg per day, but for many patients, the precise daily amount differs from either of these values since doses must be tailored to the individual patient’s response and therapeutic goals and rounded to the nearest half-tablet. Study participants will be assigned to Group A or Group B depending on which end of the range their Ferriprox intake is closer to, with equal numbers of patients enrolled in each group:

- Group A, low dosage: Patients currently taking Ferriprox tablets at a dosage that is closer to 75 mg/kg/day (n=15)
- Group B, high dosage: Patients currently taking Ferriprox tablets at a dosage that is closer to 100 mg/kg/day (n=15)

In each group, participants will be provided with deferiprone DR tablets to be taken twice daily (b.i.d.) for 28 days at a total daily dosage that matches the total amount of Ferriprox they have been taking three times daily (t.i.d.) as closely as possible. Individual doses will be rounded to the nearest 500 mg half-tablet. Doses are always to be taken with food. Following the last dose, patients will return to their regular chelation regimen.

Screening will be conducted within 14 days prior to the start of dosing, and with the exception of hematology, laboratory results obtained at that time will be treated as the baseline values. Blood samples will be collected for the assessment of biochemistry (screening and Days 3, 7, 14, 21, and 28), hematology (screening, baseline, and Days 7, 14, 21, and 28), serology (screening only), and other safety parameters (screening and Day 28); and urine samples will be collected for urinalysis (screening and Day 28). For the Day 3, 7, 14, and 21 samples, patients may choose to visit a local laboratory instead of the study site; if this is done, they must use the same laboratory throughout the entire study. If deemed necessary, patients with ongoing adverse events may be asked after the last dose to provide further blood samples for up to 30 days or until resolution. On Day 28, patients will be asked for their views on the acceptability of the delayed release formulation vs. the immediate release (Ferriprox) tablets. Any patient who withdraws before completing treatment will be requested to return for an Early Termination visit, at which time the procedures scheduled for the Day 28 visit will be conducted.

As this will be the first time that deferiprone DR is administered to patients with iron overload, as a precaution, enrollment will be conducted progressively in small groups, and safety results will be reviewed following the enrollment of a limited number of patients. Decisions regarding continuation will be based on the findings. Details are provided in [Section 3.1.1](#).

### **3.1.1 Precautions Regarding Enrollment**

The process to be followed with respect to enrollment is described below.

#### **3.1.1.1 Criteria for Safety Concerns**

As a consequence of liver iron overload and frequent blood transfusions, patients in the target population may have fluctuations of AST and/or ALT that frequently exceed the reference ranges. In recognition of this variability, for each of these enzymes, the criteria for deciding whether an individual patient's increases during the current study is of concern will be set as follows:

- For a patient whose baseline level is within the normal range, the criterion will be reaching a value of 5 times the ULN during the study.
- For a patient whose baseline level is above the ULN, the criterion will be reaching a value of 5 times the baseline value during the study or 10 x ULN.

All cases of patients meeting either of the above criteria at any point during the study must be reported to ApoPharma by the investigator within 24 hours of occurrence, using the sponsor's SAE form.

If at any time during the study a patient's ALT and/or AST values reach a level of **10 x ULN**, do the following:

- If the patient is symptomatic and/or has any other clinically significant abnormal laboratory results, immediately withdraw the patient from the study.
- If the patient is asymptomatic and has no other clinically significant abnormal laboratory results, interrupt treatment and obtain a confirmatory count the next day.
  - If the value is confirmed to be  $\geq 10$  x ULN:
    - Stop treatment, withdraw the patient and complete all end of study assessments scheduled for Day 28
    - Document the event and report it within 24 hours to ApoPharma
    - Monitor the patient daily until the elevated value returns to a level that is regarded as not clinically significant
  - If the confirmatory value is found to be  $< 10$  x ULN, resume treatment as per protocol, and monitor liver enzyme levels within 3 days of resuming therapy.

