      - If two or more patients experience a confirmed elevation of ALT and/or  $AST \geq 10 \times ULN$ , treatment is to be interrupted for all patients, and the safety committee must promptly meet to review all available safety data and recommend whether or not the study should continue

Repeat assessments to confirm laboratory results may be performed. The decision on whether to put the study on hold or terminate it will be made by the safety committee.

If a confirmed elevation of ALT and/or AST > **10 x ULN** is experienced by **two subjects in the same dosage group**, a review of the data must immediately take place to decide whether or not the study should continue. The investigator must report any occurrence of this to the sponsor within 24 hours of occurrence, using the sponsor's SAE form.

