#### **4.5 Patient Withdrawal**

Patients have the right to withdraw from the study at any time and for any reason without consequence to future care by the investigator or study center.

A patient may be withdrawn from the study at any time, at the discretion of the investigator, for any of the following reasons:

- Medical or safety reasons considered significant by the patient and/or the investigator
- Requirement for concomitant medication that might interfere with the evaluation of study treatment or may be contraindicated
- Receipt of a rescue medication
- Occurrence of other illnesses that might affect the patient's further participation in the study or evaluation of study treatment
- A protocol deviation that might interfere with study assessments, as judged by the investigator
- Repetitive patient non-compliance with the protocol or with instructions of the investigator
- Participation in another clinical trial at any time during the conduct of this study
- Any other situation where, in the opinion of the investigator, continuation of the study would not be in the best interest of the patient

A patient **must** be withdrawn from the study if any of the following conditions apply:

- Pregnant or planning to become pregnant (see [Section 7.1.4](#))
- A confirmed ALT or AST value  $>10 \times \text{ULN}$  (see [Sections 4.5.1.1](#) and [7.1.1.8.1](#))
- A confirmed ANC value  $< 0.5 \times 10^9$  (see [Sections 4.5.1.2](#) and [7.1.1.8.2](#))
- Occurrence of any adverse event characterized as life-threatening or disabling that is not associated with the patient's condition
- Termination of the study by the sponsor

Patients who decide to withdraw participation in the study should always be contacted, if possible, in order to ask about the reason for withdrawal, whether any adverse events (AEs) occurred, and use of concomitant medications. A withdrawn patient should return for an early termination visit and a follow-up visit. All investigational product and materials should be returned. If any AEs occurred, the investigator must attempt to follow up the outcome until resolution.

If a patient withdraws or is withdrawn before completing the study, the date and reason for the withdrawal must be entered on the source document and on the appropriate page of the electronic case report form (eCRF), and all other appropriate eCRF pages must be completed.

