##### **4.5.1.1 Elevated Liver Enzymes**

A patient who reaches an ALT and/or AST value  $\geq 10 \times \text{ULN}$  at any time during the study is to be **immediately** withdrawn if he or she is additionally symptomatic and/or has any other clinically significant abnormal laboratory results. If there are no other signs of concern, a confirmatory count is to be obtained the next day. If the value is confirmed, the patient is to be withdrawn; if it is not, the patient is to be closely monitored. Details are provided in [Section 3.1.1.1](#).

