#### **7.1.1.8.2 Neutropenia**

Individuals taking deferiprone must be monitored for neutropenia, defined as a confirmed absolute neutrophil count (ANC) less than  $1.5 \times 10^9/L$ . Categories of neutropenia are as follows:

Mild:	A confirmed ANC $< 1.5 \times 10^9/L$ but $\geq 1.0 \times 10^9/L$
Moderate:	A confirmed ANC $< 1.0 \times 10^9/L$ but $\geq 0.5 \times 10^9/L$
Severe / agranulocytosis:	A confirmed ANC $< 0.5 \times 10^9/L$

For a case of neutropenia to be confirmed, there must be 2 consecutive counts, a maximum of 3 days apart, that are both less than the specified value. If the 2 counts are not in the same severity category, a third count will be required to determine the severity. If a patient has just a single ANC value less than  $1.5 \times 10^9/L$  this is to be documented in the eCRF as an AE of "decreased ANC", but is not to be defined as neutropenia. The investigator is to use judgment as to whether the decrease is clinically significant.

In addition to having ANC monitored, patients will be advised to immediately report any symptoms indicative of infection such as fever ( $\geq 38.5^\circ C$ ), sore throat, and flu-like symptoms at any time during treatment or during the first week following treatment. They will be

provided with an emergency services card with contact information, and advised to carry it with them at all times.

Depending of the severity of neutropenia, patients will either remain in or be withdrawn from the study. The management of different severities of neutropenia is described below.

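### The closing 10 x ULN review rule counts confirmed ALT/AST elevations, but the confirmation step covers only asymptomatic patients, so the more serious cases need not trigger the mandatory review

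*Combined protocol and SAP*

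**What the plan says.** Section 3.1.1.1 sets out what happens when ALT or AST reaches 10 x ULN, in two branches.

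- Serious branch: "If the patient is symptomatic and/or has any other clinically significant abnormal laboratory results, immediately withdraw the patient from the study".
- Asymptomatic branch, with no other clinically significant laboratory result: dosing is interrupted and a confirmatory count is taken the next day. If the count is again at least 10 x ULN, the patient is withdrawn, the event is reported within 24 hours and the patient is monitored daily. If not, dosing resumes.

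Section 4.5.1.1 repeats the split. A patient at or above 10 x ULN is immediately "withdrawn if he or she is additionally symptomatic and/or has any other clinically significant abnormal laboratory results"; otherwise, "If there are no other signs of concern, a confirmatory count is to be obtained the next day".

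The last paragraph of Section 3.1.1.2 holds the study-level rule. It opens "If a confirmed elevation of ALT and/or AST" and applies above 10 x ULN in two subjects of the same dosage group. Then "a review of the data must immediately take place to decide whether or not the study should continue". Just before it, the section says: "Repeat assessments to confirm laboratory results may be performed".

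Section 4.5 lists among its mandatory withdrawal conditions "A confirmed ALT or AST value" above 10 x ULN, and refers to Section 4.5.1.1.

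**The concern.** The study-level rule depends on the word *confirmed*, and the protocol requires a confirming sample from only one of the two kinds of patient at 10 x ULN. The patient who also has symptoms or another significant abnormality, which is the more worrying picture, leaves the study without a required repeat. If *confirmed* means what it means in the asymptomatic branch, that patient does not add to the count of two.

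At stake is the order of the safeguards. Two asymptomatic same-group cases with confirmed repeats make a review compulsory, while two sicker same-group cases leave it to interpretation. The study is the first use of the DR tablet in iron-overloaded patients and pays particular attention to liver enzymes because of a Phase I signal, so its explicit trigger should be at least as firm for the serious cases.

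**Working it through.** The plan states no operating characteristic for this rule, so there is no figure to reproduce. The check is a comparison of the text.

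**1. What confirmation means for each laboratory alert.** For neutrophils there is a general definition in Section 7.1.1.8.2: "For a case of neutropenia to be confirmed, there must be 2 consecutive counts, a maximum of 3 days apart", both below the specified value. For ALT and AST there is no general definition. There is a working procedure, the next-day count, on the asymptomatic branch of Sections 3.1.1.1 and 4.5.1.1.

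**2. The two branches side by side.**

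| Step | Asymptomatic, no other significant result | Symptoms or other significant result |
|---|---|---|
| Treatment | Interrupted, stopped if confirmed | Withdrawn at once |
| Next-day repeat | Required | Not required |
| Daily enzyme monitoring | Required once confirmed | Not stated |
| Counts under the closing rule | Yes, if the repeat confirms a value above 10 x ULN | Not stated |

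**3. Does other text supply the missing confirmation?**

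- Section 3.1.1.2 permits repeats but does not require them.
- Section 4.5 expects a withdrawn patient to attend an early termination visit and a follow-up visit, and Table 5.1 includes biochemistry at early termination. No next-day timing is set.
- Section 4.5.1 asks for careful monitoring of alert events. Section 7.1.1.2 makes the investigator responsible for supplemental investigations. The notes in Section 7.1.2 require follow-up to resolution. None of these fixes when a repeat is taken or links it to confirmation.
- Later values will be off drug. Section 1.1 reports that Phase I enzyme levels returned to normal after the last dose, so a later sample may already be below 10 x ULN.

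**4. Does other text deem these cases confirmed?** Section 4.5 comes closest. Its mandatory withdrawal condition uses the word *confirmed* and refers to Section 4.5.1.1, which contains both branches. An inclusive reading is therefore possible. But Section 4.5.1.1 itself uses the word for the result of the next-day count, which is the narrow sense. The text does not decide between them.

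**5. When the closing rule matters.** If the first five patients in Group A are clear at one week, the rest of that group may enroll. If Group B is first and clear, all remaining patients may enroll. The other 10 x ULN rule in Section 3.1.1.2 applies only after 2 of 5 and then 4 of 10 patients have reached the criteria. It is also nested under asymptomatic patients who are still dosing, so the gap affects it only secondarily. After a clear first review, the closing rule is the explicit numerical trigger for severe elevations in the cleared group.

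**6. What still works without confirmation.**

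- Any value of 10 x ULN meets a criterion in Section 3.1.1.1: it exceeds 5 x ULN for a normal baseline and reaches the 10 x ULN limb for a raised one. It must be reported to the sponsor within 24 hours (Sections 3.1.1.1 and 7.1.1.8.1).
- The 2-of-5 and 4-of-10 gates count patients who reach the criteria, confirmed or not.
- The primary endpoint in Section 9.1.1 counts any post-dose occurrence, so its estimate and confidence interval are unaffected.

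**7. How often.** The documents give no rate of 10 x ULN elevations on DR in patients, and no share falling on the serious branch. Two figures suggest rarity. The highest value reported in Section 1.1, from a Phase I study then still in progress, was 8 x ULN, without symptoms. Section 1.2 reports that 5 of 889 patients stopped deferiprone because of liver enzymes: 5 / 889 = 0.56%. Neither is the rate needed, so no probability is calculated.

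**The case against.** The strongest reply is that the plan already handles these cases. The serious branch is the stricter one for the individual, and immediate withdrawal is right. Section 4.5 can be read so that *confirmed* covers both branches; otherwise the immediate withdrawals required by Section 4.5.1.1 would be missing from its mandatory list. Follow-up provisions make later enzyme values likely, and confirmatory repeats are allowed. The sponsor's medical and safety leads and the principal investigators sit on the safety committee (Section 8), which may hold or stop the study. Harm needs two serious-branch patients in one group of 15, at least one without a qualifying repeat, and a committee that chooses not to review after two reports on the SAE form.

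Most of this stands, and it keeps the consequence small. It does not remove the gap: discretion and a possible reading are weaker than a stated trigger, and nothing in the protocol explains why the trigger should be weaker for the sicker patient. Requiring confirmation makes sense for an isolated value in a population with fluctuating enzymes, less so for a value accompanied by symptoms or another abnormality.

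Some stronger inferences should be resisted.

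- A reader might infer that confirmation is wholly undefined for ALT and AST. It is not: the asymptomatic branch has a working procedure.
- A reader might infer that serious cases are definitely excluded from the count. The text leaves this open.
- A reader might take the one-month limit for the early termination visit (Section 5.1, Baseline Visit) as the allowed delay for a repeat. That instruction addresses patients who themselves decide to withdraw, and it asks them to come as soon as possible.

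**Conclusion.** The point holds as a gap in what is mandatory. Read literally, the closing rule of Section 3.1.1.2 does not assure a review for two same-group patients at 10 x ULN who were withdrawn at once, although it does for two confirmed asymptomatic cases above that level. The conclusion rests on two features of the text: no repeat is required on the immediate-withdrawal branch, and no sentence treats those cases as confirmed.

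Severity is minor. A reader might infer that such cases could go unnoticed, or that the primary result is affected; 24-hour reporting and a confirmation-free endpoint rule out both. Nor can a size be put on the gap by counting combinations of branches or by assuming event rates, because the documents do not say how likely each branch is. The view that such cases are rare is a judgment from the indirect figures above. The change is still worth making, because it is cheap and puts the trigger in the right order.

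**What to change.** In the last paragraph of Section 3.1.1.2, make the review mandatory when two patients in the same dosage group each have either (a) an ALT or AST value of at least 10 x ULN confirmed by the next-day repeat in Section 3.1.1.1, or (b) any value of at least 10 x ULN that led to immediate withdrawal under that section. Using *at least* aligns the rule with the confirmatory threshold in Section 3.1.1.1 and with Section 4.5.1.1.

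In Sections 3.1.1.1 and 4.5.1.1, extend the next-day repeat and the existing daily enzyme monitoring to the immediate-withdrawal branch. Withdrawal stays unconditional and does not wait for the repeat. Section 4.5.1.2 already stops drug at once and samples the next day for a single ANC below 0.5 x 10^9/L. It is a precedent for that sequence only, since there the second count also decides permanent withdrawal. The repeat would also supply a value for the nested 10 x ULN rule.

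The cost is a few words in three sections and a few blood samples for each patient concerned. The downside is an occasional extra review prompted by a spurious value in a symptomatic patient, which the next-day sample would help the committee to recognize quickly.

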### **3.1.1.2 Rules for Enrollment**

The rules that will be applied for enrolling patients in each group are described below, using the criteria provided in [Section 3.1.1.1](#). Decisions will be made by a safety committee whose composition is described in [Section 8](#).

Sites will enroll and start the dosing of patients in both groups. Once enrollment has reached **5 patients in either group**, enrollment will be paused, the safety data of those 5 patients will be reviewed by the safety committee after all 5 have completed at least one week of dosing, and further enrollment will depend on whether the findings are satisfactory or raise safety concerns.

If the first group to reach an N of 5 is **Group A** (low-dosage):

- If there are no safety concerns after one week of dosing, the safety committee will issue approval for enrollment of all remaining patients in Group A and enrollment in Group B up to 5 patients. (The criteria for enrollment in Group B are described below.)
- If 2 or more of the first 5 patients in Group A reach the criteria defined in [Section 3.1.1.1](#), the committee will issue approval for enrollment of just 5 more patients in Group A, and enrollment in Group B will be put on hold. Dosing of the first 5 Group A patients will continue, and the committee will review the data of the 10 Group A patients once all of them have completed at least 1 week of dosing.
  - At this point, if there are no safety concerns, the committee will issue approval for enrollment of the final 5 patients in Group A and for enrollment of Group B to resume, as per the criteria described for that group.
  - If 4 or more of the 10 patients in Group A who have been dosed to date reach the criteria defined in [Section 3.1.1.1](#), enrollment of additional patients in both groups will be put on hold, and the following processes are to be conducted:
    - Any patients who have reached the criterion and are symptomatic and/or have other associated abnormal laboratory values are to be withdrawn from the study.
    - Patients who did not reach the criterion and for whom there are no other safety concerns should continue dosing.
    - Patients who did reach the criterion but are asymptomatic and do not have any other associated abnormal laboratory values should continue dosing, but must have their enzyme levels monitored every 2 days:
      - If just one patient experiences a confirmed elevation of ALT and/or  $AST \geq 10 \times ULN$ , that patient is to be withdrawn from the study, but enrollment of the final 5 Group A patients may proceed.
      - If two or more patients experience a confirmed elevation of ALT and/or  $AST \geq 10 \times ULN$ , treatment is to be interrupted for all patients, and the safety committee must promptly meet to review all available safety data and recommend whether or not the study should continue.

If the first group to reach an N of 5 is **Group B** (high-dosage):

- If there are no safety concerns after one week of dosing, enroll all remaining patients in the study.
- If 2 or more of the first 5 patients in Group B reach the criteria defined in [Section 3.1.1.1](#), the committee will issue approval for enrollment of just 5 more patients in Group B. Dosing of the first 5 Group B patients will continue, and the committee will review the data of the 10 patients once all of them have completed at least 1 week of dosing. (Enrollment may continue in the meantime in Group A, provided the stopping criteria defined for that group are not met.)
  - At this point, if there are no safety concerns, the committee will issue approval for enrollment of the final 5 patients in Group B.
  - If 4 or more of the 10 patients in Group B who have been dosed to date reach the criteria defined in [Section 3.1.1.1](#), enrollment of additional patients in Group B will be put on hold, and as the processes described below are to be conducted. (Enrollment may continue in the meantime in Group A, provided the stopping criteria defined for that group are not met.)
    - Any patients who have reached the criterion and are symptomatic and/or have other associated abnormal laboratory values are to be withdrawn from the study.
    - Patients who did not reach the criterion and for whom there are no other safety concerns should continue dosing.
    - Patients who did reach the criterion but are asymptomatic and do not have any other associated abnormal laboratory values should continue dosing but must have their enzyme levels monitored every 2 days:
      - If just one patient experiences a confirmed elevation of ALT and/or  $AST \geq 10 \times ULN$ , that patient is to be withdrawn from the study, but enrollment of the final Group B patients may proceed.
      - If two or more patients experience a confirmed elevation of ALT and/or  $AST \geq 10 \times ULN$ , treatment is to be interrupted for all patients, and the safety committee must promptly meet to review all available safety data and recommend whether or not the study should continue

Repeat assessments to confirm laboratory results may be performed. The decision on whether to put the study on hold or terminate it will be made by the safety committee.

If a confirmed elevation of ALT and/or AST > **10 x ULN** is experienced by **two subjects in the same dosage group**, a review of the data must immediately take place to decide whether or not the study should continue. The investigator must report any occurrence of this to the sponsor within 24 hours of occurrence, using the sponsor's SAE form.

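### The 10-patient review and 4-of-10 enrolment hold can be reached only if 2 or more of a group's first 5 met the liver-enzyme criterion, and exactly 1 of 5 fits neither branch clearly

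*Combined protocol and SAP*

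**What the plan says.** Section 3.1.1.2 pauses enrolment once either dosage group reaches 5 patients. Their data are "reviewed by the safety committee after all 5 have completed at least one week of dosing".

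- **Release, Group A first.** If there are no safety concerns, "the safety committee will issue approval for enrollment of all remaining patients in Group A". The same sentence opens Group B only up to 5 patients, under Group B's own criteria.
- **Release, Group B first.** "If there are no safety concerns after one week of dosing, enroll all remaining patients in the study".
- **Restricted branch.** This opens with "If 2 or more of the first 5 patients in Group A reach the criteria defined in" Section 3.1.1.1, and has a Group B counterpart, "If 2 or more of the first 5 patients in Group B reach the criteria defined in" the same section. Only 5 more patients may then enter that group. For Group A, "the committee will review the data of the 10 Group A patients once all of them have completed at least 1 week of dosing". The hold follows as a sub-item: "If 4 or more of the 10 patients in Group A who have been dosed to date reach the criteria defined in" Section 3.1.1.1, enrolment stops in both groups. The Group B sub-item has the same threshold but stops Group B only.

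Some rules apply on every path. Each patient meeting a criterion is reported to the sponsor within 24 hours (Section 3.1.1.1). Two confirmed values above 10 x ULN in the same dosage group require an immediate review, and the safety committee decides on holding or terminating the study (end of Section 3.1.1.2). Section 8 has the committee review data at specified time points. Section 9.4.2 plans no interim analysis.

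**The concern.** The 4-of-10 threshold is nested inside the 2-of-5 branch, so whether it operates depends on the order of events as well as their number. Two of the first 5 followed by two of the next 5 leads to an enrolment hold. One of the first 5 followed by three of the next 5 gives the same 4 of 10, but if the 1 of 5 was released, no count-based rule responds.

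The handling of exactly 1 of 5 is itself unclear. It falls below the threshold for the restricted branch. Yet that patient has met a criterion set out in a section titled Criteria for Safety Concerns, so it is doubtful that the release condition is satisfied.

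This matters because the study is the first use of the DR tablet in iron-overloaded patients, progressive enrolment is its stated precaution (Section 3.1), and the criterion being counted is the primary endpoint (Section 9.1.1).

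**Working it through.** The plan gives no hold probability or error rate for these rules (Section 9.2 has no power calculation), so there is no figure of its own to reproduce.

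**Inputs.** The looks at 5 and 10 patients and the thresholds of 2 of 5 and 4 of 10 are from Section 3.1.1.2. The per-patient rate p is an assumption, because the documents give none for patients on DR. The nearest figure is in Section 1.1: in the healthy-volunteer study LA60-0118, about 20% of subjects dosed to date at 100 mg/kg/day reached about 5 x ULN. Rates of 10%, 20% and 40% are shown.

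**Model.** X1 is the number meeting the criterion among the first 5 and X2 the number among the next 5. They are independent binomials, with each patient's status fixed by the time of the look.

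**Step 1: order of events.** Exactly 4 of 10 can arise in 210 arrangements. By split between the first and second five: 0+4 has 5, 1+3 has 50, 2+2 has 100, 3+1 has 50 and 4+0 has 5. So 155 of 210 (73.8%) reach the hold. The other 55 (26.2%) have 0 or 1 in the first five, and 50 of those 55 start with 1 of 5.

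**Step 2: probability of 4 or more of 10 with no hold rule.**

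P(X1=0) × P(X2≥4) + P(X1=1) × P(X2≥3), where P(X1=0) = (1−p)^5 and P(X1=1) = 5p(1−p)^4.

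| Assumed p | Start at 0 of 5 | Start at 1 of 5 | Total |
|---|---|---|---|
| 10% | 0.59049 × 0.00046 = 0.0003 | 0.32805 × 0.00856 = 0.0028 | 0.0031 |
| 20% | 0.32768 × 0.00672 = 0.0022 | 0.40960 × 0.05792 = 0.0237 | 0.0259 |
| 40% | 0.07776 × 0.08704 = 0.0068 | 0.25920 × 0.31744 = 0.0823 | 0.0890 |

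Totals come from unrounded products. If 1 of 5 counts as a release, the Total column applies. If only 0 of 5 is released, the first column applies. At 40% the 1-of-5 branch supplies 0.0823 / 0.0890, about 92% of the total.

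**Step 3: effect of a check on every path.** The hold as written has probability P(X1≥2 and X1+X2≥4). A check on every path has probability P(X1+X2≥4).

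| Assumed p | Hold as written | Check on every path | Difference |
|---|---|---|---|
| 10% | 1.0% | 1.3% | 0.3 points |
| 20% | 9.5% | 12.1% | 2.6 points |
| 40% | 52.9% | 61.8% | 8.9 points |

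**The case against.** The strongest reply is that a staged rule which relaxes after a good early look must depend on the order of events, and that oversight does not end at release. Much of this stands.

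- **A reader might infer that 4 of 10 on the released path triggers nothing.** The documents do not support that. Individual reports go to the sponsor within 24 hours, two confirmed values above 10 x ULN in one group force a review, the committee can hold the study at its discretion, and Section 8 gives particular weight to the number of patients meeting the criteria. What is missing is a trigger tied to the count. The criterion can be met at 5 x ULN or 5 x baseline, so the 10 x ULN rule does not stand in for it.
- **A reader might infer that one low early count removes all count-based protection for the rest of the trial.** That is not so when Group A is first, because Group B, the high-dosage group, keeps its own 5-patient check and later hold. Only the Group B-first release covers everyone remaining.
- **A reader might take every 0-or-1-of-5 result as released** (33.7% of trials at a 40% rate). The text clearly releases only 0 of 5 (0.07776, or 7.8%, at that rate). Treatment of 1 of 5 is open, and most of the calculated effect rests on it.
- **The 40% rate has no source in the documents.** Section 1.2 hypothesises a weaker effect in patients than in healthy volunteers.
- **The gain in Step 3 assumes the count matures before later patients enter.** Without a routine pause, some of patients 11 to 15 may already be enrolled when the limit is reached.

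The reply does not remove the nesting itself or the gap at 1 of 5. Both are in the text for both groups.

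**Conclusion.** The point holds in a limited form. The plan's only count-based hold is conditional on 2 or more of a group's first 5, and the plan does not clearly say what happens at exactly 1 of 5, a result with probability 41% at an assumed 20% rate.

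The size is modest. If 1 of 5 is released, 4 or more of 10 with no hold rule has probability 0.3%, 2.6% and 8.9% at rates of 10%, 20% and 40%. If only 0 of 5 is released, it is 0.2% at 20% and 0.7% at 40%. These figures rest on assumed rates, independence between patients, and status settled by each look.

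One feature lies outside the model. The first look comes after about a week, while the criterion counts any value during the study, with enzymes measured to Day 28. Late elevations among the first 5 could add to a count that nothing uses.

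This is an inexpensive improvement to a safety rule. It does not show that patients would go unmonitored.

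**What to change.** Reconcile the branches in Section 3.1.1.2 with two statements:

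1. Which branch applies when exactly 1 of the first 5 patients meets the criterion. That choice belongs to the sponsor and the safety committee.
2. That the existing 4-of-10 enrolment check applies in each group as a running count, whatever the first-5 result, using the 24-hour reports already required.

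Enrolment need not pause while the count is below the limit. The 2-of-5 and 4-of-10 thresholds do not change, nor does the management of individual patients. The added text should say that it concerns enrolment only, because the present 4-of-10 item also carries patient-level steps.

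The cost is a sentence or two and a slightly higher chance of a pause when the true rate is low: about 0.3 points at 10% and 2.6 points at 20%. Within the model these differences, and the 8.9 points at 40%, are upper bounds on what the change can achieve, for the accrual reason given above.
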